 - b. To solicit feedback from experts in correctional mental health, addiction, and yoga; and
 - c. To modify our existing yoga treatment manual, health education manual, and instructor fidelity scales.
2. **Phase 2:** To conduct a pilot randomized clinical trial ($n = 40$) of hatha yoga vs. a health education group (attention control) for prisoners high in self-reported anger dysregulation. Participants will be enrolled in the active intervention for 10 weeks, and then be followed for 8 weeks.
 - a. To assess feasibility and acceptability of both the yoga class and the health education control group. We will assess credibility of the assigned intervention and expectancy for improvement for both groups at baseline, program satisfaction following program participation, participant adherence, ability to hold group classes (with a certain number of participants), and instructor fidelity to the manuals. We will conduct structured interviews following program participation to further understand and develop strategies to improve acceptability and feasibility.
 - b. To assess safety, we will track all adverse events in a structured fashion. We do not expect to see any serious adverse events definitely or probably related to study participation.
 - c. To assess feasibility of research procedures, we have benchmarks for recruitment rate, retention for study assessments, and reliability of instructor fidelity measures.

If successful, this project will provide us with materials, experience, and pilot data needed for the next step in this research, namely, a fully powered randomized clinical trial with anger dysregulation as the primary outcome.

Design and Outcomes

In Phase 1, we will conduct focus groups with prisoners and representatives from important criminal justice stakeholder groups (separately). We will also conduct individual interviews with prison administrators as key informants.

In Phase 2, we will conduct a pilot randomized clinical trial ($n = 40$) of hatha yoga vs. a health education group (attention control) for prisoners high in self-reported anger dysregulation. Participants will be enrolled in the active intervention for 10 weeks, and then be followed for 8 weeks. We will assess feasibility and acceptability of both the yoga class and the health education control arm, safety, and feasibility of research procedures.

In both programs, participants be involved in the study for approximately 15 hours over 18 weeks.

Interventions and Duration

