In Phase 2, we will consent up to 175 prisoners in order to achieve our enrollment goal of 40 prisoners who meet study inclusion for randomization to conditions in the pilot RCT. Participants will be recruited from the Rhode Island Department of Corrections (RIDOC) in Cranston, RI. They will be randomized to either the yoga intervention or the health education group. The study research assistant will randomize participants in the prison using small opaque envelopes labeled with a number and the strata (for example, male medium 1, male medium 2, etc.). Depending on group assignment, participants will be invited to participate in 10 weekly sessions of yoga or the health education group, to be held in the facility where they reside. Group classes will be held in relevant spaces in the facilities at RIDOC (i.e. classrooms, chapels, library, etc.). The hatha yoga intervention will involve an initial individual session with a yoga teacher, designed to increase motivation for yoga class attendance and self-efficacy for adapted yoga practice between classes. Following the initial individual session, participants will be invited to attend one 60-75 minute yoga class for 10 weeks in the prison facility where they reside. Registered yoga teachers will deliver the intervention. The Health education control group will be a 10-week program that consists of weekly 60-75 minute group classes in the prison facility where the participants reside. In classes, instructors will provide information about general health topics through a variety of means such as slides, handouts, and/or audio and video clips. This class will be taught by instructors with experience working in correctional settings and post-baccalaureate experiences or certification in a relevant health care field. In addition to the baseline assessment, outcome assessments will occur at 5 weeks (mid-intervention), 10 weeks (post-intervention), 14 weeks (qualitative interview for yoga participants only), and at 8 week follow-up, for a total length of participation of each individual participant of 4.5 months. Enrollment period for this phase will last approximately 7 months.

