Phase 1 (Focus Group) Exclusion Criteria – Stakeholders

None.

4.3 Inclusion and Exclusion Criteria, Prisoners, Phase 2.

Participants must meet all of the relevant inclusion criteria to participate in the study.

Phase 2 Inclusion Criteria – Prisoners

1. Age 18-70;
2. Clinically significant anger dysregulation, as evidenced by a score ≥ 86 on the Novaco Anger Scale (NAS);
3. Prisoner or jail detainee, with anticipated duration of remaining time incarcerated of 90 days or more, allowing for participation in the 10 week intervention;
4. Ability and willingness to provide informed consent; and
5. Willingness to be audio recorded in the intervention condition sessions (e.g., yoga or health education groups).

Phase 2 Exclusion Criteria – Prisoners

1. Presence of current manic or psychotic symptoms, or suicide risk (warranting referral to prison mental health clinical staff);
2. Any endorsed item on the Physical Activity Readiness Questionnaire (PAR-Q) except for item 6 (i.e., participants can be included even if they endorse item 6);
3. Current weekly yoga practice or current participation in mindfulness- based programming;
4. Pregnancy; and
5. Inability to understand English sufficiently well to understand the consent form or assessment instruments when read aloud.

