4.4 Study Enrollment Procedures

4.4.1. Recruitment and Screening – Prisoner Participants.

Recruitment will follow procedures successfully used to recruit prisoners into our completed and ongoing trials at the study site over the past decade. Participants will be recruited from the women's combined minimum and medium security prison and the men's medium security prison facilities of the RIDOC in Cranston, RI (see letter of support). Recruitment will occur in one of four ways. First, with permission from prison treatment staff and security personnel, research staff will make announcements to inmates to briefly explain the study (i.e. in housing units, medical units, etc.). Research staff will either individually approach inmates to assess their level of interest in the study, or hand out "interest slips" of paper, on which participants can confidentially indicate interest or lack of interest in learning more about the study. We request that all prisoners complete the "interest slip," regardless of interest in participation, to ensure privacy of responses. Second, we will identify potentially eligible participants based on their time in prison and release dates from prison records and approach them privately. This information is already publicly available (http://www.doc.ri.Gov/inmate_search/search.php), but is often provided to us in list form by the Deputy or his/her assistant for greater ease in identifying individuals who are not anticipated to be released within 90 days. Third, with the assistance of behavioral health leadership at the RIDOC, with whom we have a long history of collaboration, we will provide an in-service to prison psychiatrists and mental health counselors, and distribute study brochures so that they may refer potentially eligible participants to the study. Brochures will contain study details and guidance regarding how a participant can confidentially request more information about the study. To further minimize risk of coercion, we will not solicit direct referrals from prison mental health or other staff. Fourth, we will post flyers in each recruitment facility indicating that interested prisoners should submit an "interest slip" to learn more about our study.

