
Given study inclusion criteria, we think it unlikely that anyone will be released into the community while participating in the study. However, we do have procedures in place for people post-release. During the post-release period, definitions of suicide risk, and homicide risk will be the same those described above; however, we will rely upon our standard study procedures (vs. RIDOC mandatory/ voluntary reporting criteria) to facilitate clinician referral and safety assessment, as needed. If any study staff member identifies an individual who reports any suicidal or homicidal ideation in the course of standard assessment procedures, the staff member will immediately contact [name] or [name] (or the licensed covering clinician). The covering clinician will evaluate the participant over the telephone or in person. First, they will conduct a suicide and homicide risk assessment to determine whether it is necessary to take immediate action to prevent the participant from causing harm to self or others. If needed, actions that the covering clinician may take include escorting the person to the emergency Patient Assessment Service (PAS) at Butler Hospital (if the person is in our offices), having a family member transport the person to Butler Hospital or another hospital, or sending an ambulance so that the individual may be evaluated for inpatient psychiatric hospitalization.

A participant who has undergone a suicide or homicide risk assessment may continue to participate in the study unless the study PIs, in concert with the participant's healthcare providers, deem study participation to increase risk for this particular participant.

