Feasibility and Acceptability—Research Procedures	
Recruitment rate	Average of 6 enrolled per month
Retention rate	80% complete week 10 assessment; 70% complete wk. 18 assessment
Completion of items on assessment instruments	At least 90% of items are completed on each assessment instrument (so each will be valid).

9.5.2 Secondary/ Exploratory Outcomes.

In Phase 2, we will also examine change in key variables over time. This is an exploratory analysis.

Specifically, we will look at change over time the in the following variables. The primary outcome in a subsequent efficacy study is in **bold and underlined**. Secondary outcomes are in standard text. *Potential mechanisms are in italics*.

- **NAS-Provocation Inventory from BL to wk10**; BL to wk18.
- Aggression Questionnaire – Short Form, BL to wk10; BL to wk18.
- Number of behavioral infractions in Prison, BL to wk10; BL to wk18
- PHQ-9, BL to wk10; BL to wk18
- PROMIS Anxiety, BL to wk10; BL to wk18
- SF-12 physical health composite score, BL to wk10; BL to wk18
- SF-12 mental health composite score, BL to wk10; BL to wk18
- *Anger rumination scale, BL to wk10; BL to wk18*
- *Experiences Questionnaire, BL to wk10; BL to wk18*

- *Stroop Color and Word Test, BL to wk10; BL to wk18*

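### The inclusion criteria do not support the statement that release during participation is unlikely: they require 90 days remaining in custody, and participation runs 126 days

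*Combined protocol and SAP*

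**What the plan says.** **The expectation.** Protocol section 7.1 (Protection Against Risks, item 2) gives the inclusion criteria as the reason for its view: "we think it unlikely that anyone will be released into the community while participating in the study". DSMP section 5, under suicide or homicide ideation, repeats the sentence. Item 3 of the same part of section 7.1 calls release before the end of the study rare. DSMP section 5, under confidentiality, treats it as an unanticipated consequence of a shortened sentence.

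**The criterion.** Section 4.3, Phase 2 inclusion criterion 3, reads: "Prisoner or jail detainee, with anticipated duration of remaining time incarcerated of 90 days or more, allowing for participation in the 10 week intervention". Section 4.4.1 applies the same cut-off to the recruitment lists, which are used for "identifying individuals who are not anticipated to be released within 90 days".

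**The length of participation.** The Précis says: "Participants will be enrolled in the active intervention for 10 weeks, and then be followed for 8 weeks". It also has participants "involved in the study for approximately 15 hours over 18 weeks". Section 3 describes the schedule as "for a total length of participation of each individual participant of 4.5 months". Table 3 schedules assessments at weeks 5, 10 and 18, and a week 14 interview for yoga participants only.

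**What runs to week 18.** The target outcomes table in section 9.5.1 sets retention at "80% complete week 10 assessment; 70% complete wk. 18 assessment". Section 9.5.2 lists the change in the number of prison infractions from baseline to week 18.

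**Other statements on release.** Section 4.4.3 accepts that some participants may be released before they finish, and asks for permission to locate them. Sections 6.2.6, 6.4, 7.1 and 8 deal with follow-up, payment, safety contact and continued assessment after release.

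**The concern.** The criterion explains its own purpose: it secures the 10-week course. The safety text then relies on it for the whole of participation, which is 8 weeks longer. Someone who is fully eligible can have a scheduled release date before the last assessment, with no sentence reduction and nothing unexpected happening. The protocol and DSMP therefore state a property that the design does not have, and section 4.4.3 already says something different.

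Three things are affected:

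- **Week 18 retention.** After release, follow-up depends on reaching the participant in the community, and section 4.4.3 lets participants refuse or revoke permission to be located.
- **Mode of assessment.** Section 6.2.6 aims for telephone assessment after release, so week 18 data can differ in mode from baseline data. How the Stroop task due at week 18 would be given by telephone is not described.
- **Prison infractions.** A released participant can no longer commit one. Table 5 plans within-group comparisons with baseline, so a fall in the count caused by lost custody time would look like improvement in whichever arm it occurred. Randomization does not protect a within-group comparison from this.

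**Working it through.** **Inputs.** Minimum remaining time, 90 days (section 4.3). Intervention 10 weeks plus follow-up 8 weeks (Précis). Classes may start up to one week after randomization (section 6.2.4). Assessment window of one week either side (section 6.2.6). Randomized sample of 40 (section 3).

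**Step 1: the plan's own duration.** 10 + 8 = 18 weeks, which reproduces the Précis. 18 × 7 = 126 days. The 4.5 months in section 3 equals 126 days if a month is four weeks. In calendar months it is 4.5 × 365.25 / 12 = 137 days.

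**Step 2: what 90 days covers.**

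| Visit | Day due | 90 minus day due |
|---|---|---|
| Week 5 | 35 | +55 |
| Week 10 | 70 | +20 |
| Week 14 (yoga only) | 98 | −8 |
| Week 18 | 126 | −36 |

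Week 10 stays covered with the start lag (70 + 7 = day 77) and with the late edge of the window added (77 + 7 = day 84). Week 18 is not covered even at the early edge of its window: 126 − 7 = day 119, which is 29 days past the minimum. Against 137 days the gap is 137 − 90 = 47 days.

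**Step 3: how many could be affected.** The documents give no distribution of remaining time. As an assumption, take it as uniform from 90 days to an upper limit U. The share below 126 days is p = 36 / (U − 90). The chance of at least one such participant among 40, treating them as independent, is 1 − (1 − p)^40.

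| U (days) | p | Expected of 40 | Chance of at least one |
|---|---|---|---|
| 180 | 36/90 = 40% | 16 | about 100% |
| 365 | 36/275 = 13% | 5.2 | 99.6% |
| 730 | 36/640 = 5.6% | 2.2 | 90% |
| 1,825 | 36/1,735 = 2.1% | 0.8 | 57% |

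**Step 4: against the retention target.** 70% of 40 is 28, so 12 may be missing at week 18. If every released participant were lost, the 365-, 730- and 1,825-day cases lose about 5, 2 and 1, all within the allowance. Only the 180-day case could miss the target through release alone, and then only if at least 13 of the 16 were lost.

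**Step 5: against the infraction count.** Sections 9.1.2 and 9.5.2 give no counting period, so two are shown, assuming a constant infraction rate in custody and release at day 90, the extreme of the band. Counting from baseline to week 18, exposure is 90/126 = 71% of full custody. Counting from week 10 to week 18, it is (90 − 70)/(126 − 70) = 20/56 = 36%. With no change in behaviour, the expected count falls in the same proportion.

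**The case against.** **The 90 days is a floor.** Most participants may have much longer to serve. The gap shows that the criteria do not secure custody through week 18; it does not show how often release happens. This stands. A reader might infer that release will be a regular cause of missing or telephone-collected week 18 data. The documents do not support that: it depends on the assumed distribution, and with U at 730 days or more the expected number is about 2 of 40 or fewer, which could fairly be called rare.

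**Release is already planned for.** Sections 4.4.3, 6.2.6, 6.4, 7.1 and 8 cover locating, assessing, paying and safety contact after release, and the DSMP has contact details updated at each assessment. This also stands. Release is not the same as missing data, and no procedure is absent.

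**Nothing is built on the sentence.** A reader might infer that it underlies the 70% retention target or the clinical cover after release. Section 9.5.1 says the targets rest on face validity, clinical experience and literature, and the sentence in section 7.1 leads straight into the post-release procedures. The expectation bears on the target; it is not shown to be its basis.

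**Jail detainees.** It is tempting to add that unsentenced detainees have less predictable release dates. The documents do not say so, and they apply the same 90-day minimum to detainees.

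**Participating might mean attending classes.** On that reading the sentence would be sound, since 90 days covers the course. It does not fit the text: section 3 puts total participation at 4.5 months, and both the rare-event remark in section 7.1 and the DSMP remark about shortened sentences refer to completion of the study.

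**Conclusion.** The point holds as an internal inconsistency and an unsupported stated expectation. The criteria make release unlikely through the 10-week intervention. They do not do so through week 18, where they fall 36 days short, and anyone with 90 to 125 days remaining is expected at entry to leave before the final visit. That part rests only on the documents' own figures.

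The frequency is unknown. The range of about 2% to 40% (1 to 16 of 40) rests entirely on the uniform assumption and the chosen upper limits. It is therefore not established that release will be common, or that the retention target is at risk. The firmest analytic consequence is the infraction count to week 18: time out of custody carries no in-prison exposure, and no allowance for this is stated.

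**What to change.** 1. **Reword four statements** so that they agree with sections 4.3 and 4.4.3: the two in protocol section 7.1 (items 2 and 3) and the two in DSMP section 5 (suicide or homicide ideation; confidentiality). They should say that the criteria cover the intervention period and that participants with 90 to 125 days remaining are expected to be released before week 18. Changing only the repeated sentence would leave the rare-event and shortened-sentence remarks in conflict with it.
2. **Record the expected release date at baseline.** Remaining time is already established for eligibility, so this means keeping a value that staff have in hand.
3. **Report week 18 retention and mode of assessment by custody status**, as simple counts.
4. **Report infractions with days in custody as the exposure**, or restrict the count to time in custody, and state the counting period.

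The 90-day criterion and the existing post-release provisions need not change. The cost is four edited statements, one baseline field and a small amount of descriptive reporting, including days in custody for each participant. The stated expectation about release becomes less favourable. In an unpowered pilot the breakdowns are descriptive only, but they would show how much of any week 18 loss or fall in infractions reflects release.
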